- m. Remote contact (text message by sms, WhatsApp or email) on Day 3 and on Days 21, 31 and 49 for safety follow-up and reminder stool collection scheme.
- n. Adverse events and intake of concomitant medication(s) will be monitored continuously from informed consent until the last study-related activity. The subjects can record unsolicited AEs on their diary card.
- o. After signing on screening visit, weekly reminder Code of Conduct by email or sms and on each visit to emphasize the need and importance of hygienic measures and respecting the inclusion/exclusion criteria until end of study.

LIST OF ABBREVIATIONS AND DEFINITIONS OF TERMS

List of Abbreviations

AE	Adverse event
ALT	Alanine Aminotransferase
AMA	Anti-Mitochondrial antibodies
ANA	Anti-Nuclear antibodies
AST	Aspartate Aminotransferase
bpm	Beats per minute
CCID ₅₀	50% cell culture infective dose
CI	Confidence interval
CK	Creatine phosphokinase (including isozymes)
CRF	Case Report Form
CTCAE	Common Terminology Criteria for Adverse Events
cVDPVs	Circulating vaccine-derived polioviruses
cVDPV2	Circulating vaccine-derived poliovirus type 2
DBP	Diastolic blood pressure
DNA	Deoxyribonucleic acid
DSMB	Data Safety Monitoring Board
eCRF	Electronic Case Report Form
EDC	Electronic Data Capture
GCP	Good Clinical Practice
GGT	Gamma-Glutamyl Transferase
GMT	Geometric mean titer
GPEI	Global Polio Eradication Initiative
HBsAg	Hepatitis B surface antigen
HCV	Hepatitis C virus
HDPE	High Density Polyethylene
HIV	Human immunodeficiency virus
HR	Heart rate
ICF	Informed Consent Form
ICH	International Conference on Harmonization
IEC	Independent Ethics Committee
IME	Important medical event
IMP	Investigational medicinal product
IPV	Inactivated polio vaccine
IRB	Institutional Review Board
LDH	Lactate dehydrogenase
LKM-1	Liver-kidney microsomal type 1 (antibodies)
LSLV	Last Subject Last Visit
MedDRA	Medical Dictionary for Regulatory Activities
mOPV2	Monovalent oral polio vaccine type 2
nOPV2	Novel oral polio vaccine type 2
OPV	Oral polio vaccine
PD50	50% paralytic dose
PP	Per-protocol

RNA	Ribonucleic acid
SAE	Serious adverse event
SAGE	Strategic Advisory Group of Experts on immunization
SAP	Statistical Analysis Plan
SBP	Systolic blood pressure
SD	Standard deviation
SLA/LP	Soluble liver antigen/liver-pancreas (antibodies)
SmPC	Summary of Product Characteristics
SUSAR	Suspected Unexpected Serious Adverse Reaction
tOPV	Trivalent oral polio vaccine
TgPVR	Transgenic mice expressing the cell receptor for poliovirus

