In general, the safety data were reassuring. There were no remarkable clinical events. The primary clinical endpoints were serious (SAE) and severe adverse events: there were no SAEs; none of the solicited adverse events (pre-specified parameters during the 7 days following vaccination) were severe, and most were mild; and the severe unsolicited AEs were predominantly transient, asymptomatic abnormalities in monitoring laboratory assessments. Most unsolicited clinical AEs were mild, and all self-resolving. No severe AEs were assessed as probably related to the vaccines.

Two participants (one from each cohort) exhibited transient, asymptomatic, severe elevations of AST, both associated with mild or moderate elevation of ALT, severe elevation of CK, no elevation of either GGT or bilirubin, and with complete resolution to normal values. Other AEs on the basis of AST elevations were asymptomatic and generally mild and self-resolving, and also associated with elevated CK levels but normal GGT and bilirubin levels. All AEs on the basis of ALT elevations were transient and asymptomatic, with only one moderate AE and the balance mild. Half of the participants exhibited asymptomatic severe elevations of CK, most often at the day 7 assessment, with resolution of values elevated in the first couple of weeks post-vaccination to normal or close to normal.

Such patterns of enzyme changes have been seen with intermittent, intense exercise, which could provide an explanation for these participants suddenly restricted to a contained unit with an exercise facility for 28 days or more. However, in the absence of a control group in this study, a relationship to vaccine cannot be ruled out. As such, the subsequent study has been redesigned to further assess enzyme changes in additional participants who have not received OPV in the past, and to randomize these participants to receive either one of the vaccine candidates or placebo.

1.3.2 *Potential Benefits*

Subjects who previously completed the childhood polio vaccination schedule and receive a dose of nOPV2 in this study may have a boosted immunity for poliovirus type 2.

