11.2 INTENSITY OF ADVERSE EVENTS

Severity of solicited AEs will be scored as indicated on the Diary Card.

Each unsolicited AE must be rated on a 3-point scale of increasing intensity as outlined below:

Grade 1:

Mild; an AE that is easily tolerated by the subject, causing minimal discomfort and not interfering with everyday activities.

Grade 2:

Moderate; an AE that is sufficiently discomforting to interfere with normal everyday activities.

Grade 3:

Severe; an AE that prevents normal everyday activities. Such an AE would, for example, prevent attendance at work and would necessitate the administration of corrective therapy.

Fever will be assessed using the NIH CTCAE grading scale:

Grade 1: 37.5°C to 38.0°C

Grade 2: 38.1°C to 39.0°C

Grade 3: >39.0°C

Lab results will be assessed using the NIH CTCAE version 4.03 (toxicity grades). For grade 1 values the investigator will use his clinical judgement to determine these values as clinically significant. Lab values above grade 1 will automatically be deemed clinically significant, and recorded as adverse events.

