- **Immunogenicity:** seroprotection rate of type 2 polio antibodies at Day 28, following a single dose of mOPV2 (combined Groups 1 and 2).
Seroprotection is defined as type 2-specific antibody titers $\geq 1:8$.

Secondary

The following endpoints will be evaluated by group and overall:

Safety:

- the incidence, type, causality and severity of solicited adverse events for days 0-7 in both groups combined and days 28-35 in Group 2;
- the incidence, type, causality and severity of unsolicited adverse events throughout the study period;
- Incidence, causality and description of deviations from normal safety labs at Day 0 (both groups), Day 7 (both groups), Day 28 (both groups), Day 35 (Group 2), and Day 56 (Group 2).

Immunogenicity:

- Median titers of type 2 polio antibodies at Day 28 in Groups 1 and 2 combined;
- Seroprotection rate and median titers of type 2 polio antibodies at Day 56 in Group 2;
- Seroconversion rate of type 2 polio antibodies at Day 28 for both groups combined and at Day 56 in Group 2.
Seroconversion is defined as a change from seronegative to seropositive and antibody titers of $\geq 1:8$, and in seropositive subjects, as an antibody titer increase of ≥ 4 fold over baseline titers.

Exploratory

- GMT of type 2 polio antibodies at Day 28 in both groups combined and at Day 56 in Group 2;
- Descriptive analysis of viral shedding as determined using quantitative PCR (viral identity) and 50% cell culture infective dose (CCID₅₀; titer) after viral extraction from stool samples taken at one or more time points in a subset of stool samples;
- Exploratory endpoints may also include assessment of the genetic sequence heterogeneity and potential for neurovirulence (as measured in an animal model) of shed virus in a subset of stool samples;

Statistical Methods:**Sample size**

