3.5.2 Secondary endpoints

Safety: The following endpoints will be evaluated by group and overall:

- incidence, type, causality and severity of solicited adverse events for days 0-7 in Groups 1 and 2 combined and days 28-35 in Group 2;
- incidence, type, causality and severity of solicited adverse events for days 0-7 in Groups 3 and 4 combined and days 28-35 in Group 4;
- incidence, type, causality and severity of solicited adverse events for days 0-7 and days 28-35 in Groups 5, 6 and 7;
- incidence, type, causality and severity of unsolicited adverse events throughout the study period in all groups;
- incidence, causality and description of deviations from normal safety labs at Day 0, Day 7, Day 14 and Day 28 for Groups 1 through 4, and at Day 35, Day 42 and Day 56 for Groups 2 and 4;
- incidence, causality and description of deviations from normal safety labs at Day 0, Day 7, Day 14, Day 28, Day 35, Day 42 and Day 56 for Groups 5, 6, and 7.

Immunogenicity:

- Median titers of type 2 polio antibodies at Day 28 in Groups 1 and 2 combined;
- Median titers of type 2 polio antibodies at Day 28 in Groups 3 and 4 combined;
- Median titers of type 2 polio antibodies at Day 28 in Groups 5, 6 and 7.
- Seroprotection rate and median titers of type 2 polio antibodies at Day 56 in Groups 2 and 4;
- Seroprotection rate of type 2 polio antibodies at Day 28 and at Day 56 in Groups 5, 6 and 7.
- Seroconversion rate of type 2 polio antibodies at Day 28 for Groups 1 and 2 combined and at Day 56 in Group 2;
- Seroconversion rate of type 2 polio antibodies at Day 28 for Groups 3 and 4 combined and at Day 56 in Group 4;

- Seroconversion rate of type 2 polio antibodies at Day 28 and at Day 56 for Groups 5, 6 and 7. Seroconversion is defined as a change from seronegative to seropositive and neutralizing antibody titers of $\geq 1:8$, and in seropositive subjects, as an antibody titer increase of ≥ 4 -fold over baseline titers.

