6.5.1 Primary Safety Endpoints

- Solicited adverse events:
 - Serious/severe solicited adverse events will be summarized by group, by post-vaccination time period as well as overall (under maximum severity), and by term by post-vaccination time period as well as overall (under maximum severity), as well as listed.
- Unsolicited adverse events:
 - Serious/severe unsolicited AEs will be summarized by group, maximum causality and by class (serious vs severe) under maximum causality, by post-vaccination

time period (prior to dose 2 vs following dose 2) as well as overall, and reasons for SAE classification (wherever such subcategories are relevant), as well as by SOC and PT among serious events only (and among those serious and related), and among severe events only (and among those severe and related). These events will also be listed.

- Listings will be prepared for those subjects who died or withdrew from the study due to an AE.

Two-sided p-values from the Fisher exact test of the number of subjects with an event will be presented for:

- Severe solicited events (overall, and by event term)
- Any serious unsolicited event
- Any serious and related unsolicited event
- Any severe unsolicited event
- Any severe and related unsolicited event

These comparisons will be conducted for the following groups:

- UAM4 Groups 1 & 2 vs UAM1 Groups 1 & 2
 - Post-dose-1 and overall, TVP
- UAM4 Group 2 vs UAM1 Group 2
 - Post-dose-2, TVP subjects who received both doses
- UAM4 Groups 3 & 4 vs UAM1 Groups 1 & 2
 - Post-dose-1 and overall, TVP
- UAM4 Group 4 vs UAM1 Group 2
 - Post-dose-2, TVP subjects who received both doses
- UAM4 Group 5 vs UAM4 Group 7
 - Post-dose-1, post-dose-2, and overall, TVP
- UAM4 Group 6 vs UAM4 Group 7
 - Post-dose-1, post-dose-2, and overall, TVP

Comparisons for both solicited and unsolicited events will be conducted separately for post-dose-1 and post-dose 2, as well as following any dose. Comparisons involving post-dose-2 data will include only subjects receiving both doses.

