Clinical laboratory abnormalities will be summarized by lab parameter, time point and grade (with separate categories for high and for low values of a given lab value, where relevant), as well as in a shift table displaying the frequency of post-baseline abnormalities by grade for each time point cross-tabulated with the classification at baseline, for each time point for each lab parameter, maximum grade across lab parameter within each time point, and maximum grade across post-baseline time points and lab parameter. A separate table will summarize according to grade only those values considered to be clinically relevant. Additional summary tables will be produced including the continuous values and the change from baseline for each group and post-vaccination day. Boxplots will display the raw value by lab parameter and study collection day, and will include separate symbols to depict values out of range and those out of range and clinically relevant. A listing, including grade and clinical relevance, will also be prepared.

While all safety lab abnormalities will be summarized, for each of the specific safety lab parameters listed below, the rate of moderate or greater post-baseline abnormalities will be presented at the subject level overall as well as by timepoint, and by abnormality grade (using the maximum grade post-baseline, where relevant), and accompanied by a two-sided 90% confidence interval using the Miettinen and Nurminen method for the risk difference of each vaccine candidate vs. the comparator group: ALT, AST, CK, GGT, bilirubin and albumin. For IPV-vaccinated subjects (Groups 5 and 6), comparisons will be made relative to the placebo

group (Group 7), and for OPV-vaccinated subjects (Groups 1 – 4), comparisons will be made relative to the corresponding UAM1 control (for lab values assessed in both studies), combining groups where possible, as described above (e.g., Group 1 & 2, post-dose-1).

Pregnancy test results will be listed.

Abnormal vital signs (heart rate, systolic/diastolic blood pressure, body temperature) will be summarized by group and by time point (day, prior to/following vaccination). The summary will also include the number and percent of subjects with abnormal and clinically relevant vital signs. Vital signs will be listed, and summarized as continuous variables by time point, including change from baseline, by group, and change pre- to post-vaccination for vaccination visits.

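### Safety comparisons with UAM1 do not match laboratory draws or analytes (SAP 6.5.1) or draws (SAP 6.5.2), so laboratory-derived events are more readily counted in UAM4

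*SAP*

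**What the plan says.** SAP 6.5.1 (Primary Safety Endpoints): "Two-sided p-values from the Fisher exact test of the number of subjects with an event will be presented for" five outcomes. One is "Any severe unsolicited event" and another is its related subset. Groups 1 and 2, and Groups 3 and 4, are each tested against UAM1 Groups 1 and 2, and the two-dose groups are also tested after dose 2. Laboratory-derived events are not set apart.

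Protocol 11.2: "Lab values above grade 1 will automatically be deemed clinically significant, and recorded as adverse events". The grades are CTCAE 4.03.

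Laboratory schedule in UAM4 (SAP 3.5.2): "safety labs at Day 0, Day 7, Day 14 and Day 28 for Groups 1 through 4, and at Day 35, Day 42". The last draw in the two-dose groups is on Day 56. In UAM1 (Protocol Appendix 3) the schedule was: "at Day 0 (both groups), Day 7 (both groups), Day 28 (both groups), Day 35 (Group 2), and Day 56 (Group 2").

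SAP 6.5.2: for ALT, AST, CK, GGT, bilirubin and albumin, "the rate of moderate or greater post-baseline abnormalities will be presented at the subject level overall" and by timepoint, with a 90% Miettinen-Nurminen interval for the risk difference. Against UAM1 this is limited to analytes assessed in both studies. It is not limited to common draw days.

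Follow-up (Time and Events footnote n): "Adverse events and intake of concomitant medication(s) will be monitored continuously from informed consent until the last study-related activity". SAP 6.5 gives adverse-event summaries a start date but no end date. SAP 5.1 aligns terms and coding with UAM1, but not schedule or time window.

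**The concern.** A subject-level count of anyone with an event rises with the number of times one looks. UAM4 looks at blood three times after each dose and UAM1 looked twice. An analyte measured only in UAM4 can yield an event there and none in UAM1.

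This matters because laboratory findings may dominate the endpoint. In the first-in-human study "the severe unsolicited AEs were predominantly transient, asymptomatic abnormalities in monitoring laboratory assessments" (Protocol 1.3.1), and half the participants had severe CK elevations. Protocol 1.2.2.1 makes a safety profile similar to mOPV2 one of three licensing criteria. An excess of severe events over UAM1 could not be attributed to the vaccine rather than to sampling.

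A second, separate gap concerns time. Follow-up is extended for subjects still shedding at the end of the schedule, and their events continue to count. No such extension is described for UAM1, and none is expected in placebo recipients.

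**Working it through.** **The plan's own safety figure.** Protocol 10.2 gives 45 subjects for a 90% chance of seeing at least one event at a 5% rate: 1 − 0.95^45 = 0.9006, and 45/0.9 = 50. It reproduces and is not disputed, but it does not address a comparison between studies.

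**Draws after baseline** (SAP 3.5.2; Protocol Appendix 3)

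| | UAM4 | UAM1 |
|---|---|---|
| After dose 1 | D7, D14, D28 (3) | D7, D28 (2) |
| After dose 2 | D35, D42, D56 (3) | D35, D56 (2) |
| Two-dose total | 6 | 4 |

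**Effect of the extra draws.** Assume the same risk p at each draw in both studies, independent draws, and no vaccine effect. Half of each 100 receive one dose and half two. Calibrate to the background rate of about 6% that Protocol 10.2 takes from UAM1:

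- UAM1: ½[1 − (1−p)²] + ½[1 − (1−p)⁴] = 0.06, so p = 0.0205 (one dose 4.05%, two doses 7.95%).
- UAM4: ½[1 − (1−p)³] + ½[1 − (1−p)⁶] = ½(6.02% + 11.68%) = 8.85%.
- Ratio: 8.85/6.0 = 1.47.

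Exact enumeration of all outcomes, 100 v 100:

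| Analysis | True rates | Planned draws | Matched draws |
|---|---|---|---|
| 6.5.2, 90% lower bound > 0 | 8.85% v 6.0% | 19.7% | 5.5% |
| 6.5.1 Fisher p ≤ 0.05, overall | 8.85% v 6.0% | 7.4% | 2.4% |
| 6.5.1 Fisher p ≤ 0.05, post-dose-1 | 6.02% v 4.05% | 4.8% | 1.7% |

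**Sensitivity to the per-draw risk q** (an assumption; the documents give no per-draw rate of severe values). Post-dose-1, risk 1 − (1−q)³ v 1 − (1−q)², Fisher test:

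| q | UAM4 v UAM1 | 3 v 2 draws | 2 v 2 draws |
|---|---|---|---|
| 1% | 3.0% v 2.0% | 1.4% | 0.5% |
| 2% | 5.9% v 4.0% | 4.6% | 1.7% |
| 3% | 8.7% v 5.9% | 7.3% | 2.4% |
| 5% | 14.3% v 9.8% | 11.9% | 2.8% |
| 10% | 27.1% v 19.0% | 22.1% | 3.3% |

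After dose 1 the nominal 5% is passed only when q exceeds about 2%.

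**Effect of unmatched analytes.** Let b be the common base rate and c the share of UAM4 subjects with a severe laboratory event that UAM1 could not record. Both are assumptions. The UAM4 rate is 1 − (1−b)(1−c). Probability of a significant Fisher test against the candidate, 100 v 100:

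| c | b = 3% | b = 6% |
|---|---|---|
| 0 | 0.6% | 1.2% |
| 5% | 22% | 16% |
| 10% | 67% | 50% |

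**Follow-up.** Planned duration is the same in both studies, about 6 weeks for one dose and 10 weeks for two. In UAM4 a subject who is PCR-positive on one of the last three scheduled stools stays in the study until three consecutive negatives. The longest shedding in the first-in-human study was almost 3 months for candidate 1 and just over a month and a half for candidate 2 (Protocol 1.2.1). No scheduled safety laboratory draw falls after Day 28 (one dose) or Day 56 (two doses), so the extension affects adverse events generally and adds no scheduled laboratory tests.

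**The case against.** The strongest reply is that the plan already limits the damage. Protocol 10.1.4 calls the historical safety comparison descriptive, and no decision rule hangs on the p-values. SAP 6.5.2 also gives risk differences by timepoint, so like-for-like contrasts at Days 7, 28, 35 and 56 will exist. SAP 6.5.1 tabulates severe events by system organ class and preferred term, and the listings give onset day. Any bias in laboratory-derived events is toward a false alarm, not a missed harm. This lowers the severity. It does not correct the subject-level Fisher tests or the overall maximum-grade risk differences. The Fisher p-values also go beyond the protocol's descriptive plan and are not listed in SAP section 7.

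Equal, independent risk per draw is generous to the concern. First-in-human CK elevations were mostly at Day 7, which both studies sampled, so a Day 14 finding would often fall in a subject already counted. The 6% is for elevations of unstated grade, not severe values. Both points stand, so 8.8% is near an upper limit for the effect of extra draws at that background rate.

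The documents neither list UAM1's analytes nor say whether it used the automatic rule. They do not state outright that a grade 3 value counts as a severe event. The analyte gap is implied by Protocol 10.1.4, which compares with UAM1 where possible and names ALT and AST as examples, and by the restriction in SAP 6.5.2. The severity mapping is made plausible by how the first-in-human events were reported.

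A reader might infer that the candidates are bound to look worse overall. The documents do not support that. UAM1 had daily remote contact on Days 0–10, and again on Days 28–38 in its two-dose group; UAM4 had contact on Days 3 and 21, plus 31 and 49 in two-dose groups. That could raise UAM1's clinical event count.

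**Conclusion.** The concern holds for laboratory-derived events in two places: the 6.5.1 Fisher tests of severe unsolicited and severe related unsolicited events against UAM1, and the 6.5.2 overall risk differences against UAM1. The mismatch there can only add to the UAM4 count. The net direction across all adverse events is not established.

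Under the equal-risk assumption, extra draws alone lift an expected 6% to about 8.8%. That has a modest effect on the Fisher tests (about 7% overall and 5% post-dose-1) and a larger one on the 6.5.2 interval (about 20% against 5.5%). Unmatched analytes could produce adverse Fisher significance in 16–22% of trials (5% excess) or 50–67% (10% excess), but both the excess and the 3–6% base rate are assumed.

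Three stronger readings are not supported. The 20% does not apply to the primary Fisher test. Extended follow-up is not shown to generate laboratory-derived events. UAM1 did not lack the Day 14 visit, or Day 42 in its two-dose group; it lacked the blood draw. Solicited-event tests use the same windows in both studies. Comparisons with Group 7 share the laboratory schedule, so only the open-ended follow-up touches them.

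This should be fixed, but it does not undermine the trial.

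**What to change.** 1. **SAP 6.5.1, UAM1 comparisons.** Add Fisher rows for severe unsolicited and severe related unsolicited events (a) excluding laboratory-derived events and (b) for laboratory-derived events limited to analytes and draw days common to both studies (D7, D28, D35, D56). Base the interpretation of the historical contrast on these rows and keep the all-events row as descriptive. If UAM1 did not apply the automatic rule, build row (b) from the graded values; both studies grade by CTCAE 4.03.
2. **SAP 6.5.2.** Compute the overall maximum-grade risk difference against UAM1 from the common draw days only.
3. **Time window.** Repeat the serious and severe comparisons, including those against Group 7, counting events only through the scheduled final visit window (42 days after the last dose, plus 4 days). Keep the uncut results. A cut at exactly day 42 would clip final visits made on time.

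Keep Day 14 and Day 42 laboratory data in all UAM4 tables and in the placebo comparisons. The cost is SAP wording, programming flags for draw day, analyte and event day, and a few extra table rows. The downside is that findings seen only on Day 14 or Day 42 do not enter the matched UAM1 rows.

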6.5.2 Secondary Safety Endpoints

- Solicited AEs, collected within 7 days following vaccination, will be summarized by group overall and by term, (any event regardless of severity, and by severity according to maximum severity, across terms and for each term), for each post-vaccination time period as well as overall, as well as listed.
- Unsolicited AEs will be summarized by group, by relationship under maximum causality, by severity under maximum severity, by post-vaccination time period as well as overall, as well as by SOC and PT, and by SOC and severity (maximum severity). Separate tables by SOC and PT will be produced for moderate or greater events, and for moderate or greater related events only. A table will be produced summarizing preferred terms for those terms arising in >2% of subjects, sorted in descending order.
- A listing of AEs including verbatim term, start/stop date, timing (post-dose 1 vs post-dose 2), including post-prior-vaccination onset day, coded terms, severity, causality, actions taken, outcomes, and type (solicited vs. unsolicited) will be provided.

Clinical laboratory test values will be evaluated according to Common Terminology Criteria for Adverse Events (CTCAE) version 4.03 (toxicity grades using ranges for laboratory abnormalities) or in accordance with the normal ranges of the clinical laboratory (below, within, or above normal range) for parameters for which no toxicity grades are defined. The limits of quantitation will be substituted for the actual value, where necessary.

Clinical laboratory abnormalities will be summarized by lab parameter, time point and grade (with separate categories for high and for low values of a given lab value, where relevant), as well as in a shift table displaying the frequency of post-baseline abnormalities by grade for each time point cross-tabulated with the classification at baseline, for each time point for each lab parameter, maximum grade across lab parameter within each time point, and maximum grade across post-baseline time points and lab parameter. A separate table will summarize according to grade only those values considered to be clinically relevant. Additional summary tables will be produced including the continuous values and the change from baseline for each group and post-vaccination day. Boxplots will display the raw value by lab parameter and study collection day, and will include separate symbols to depict values out of range and those out of range and clinically relevant. A listing, including grade and clinical relevance, will also be prepared.

While all safety lab abnormalities will be summarized, for each of the specific safety lab parameters listed below, the rate of moderate or greater post-baseline abnormalities will be presented at the subject level overall as well as by timepoint, and by abnormality grade (using the maximum grade post-baseline, where relevant), and accompanied by a two-sided 90% confidence interval using the Miettinen and Nurminen method for the risk difference of each vaccine candidate vs. the comparator group: ALT, AST, CK, GGT, bilirubin and albumin. For IPV-vaccinated subjects (Groups 5 and 6), comparisons will be made relative to the placebo

group (Group 7), and for OPV-vaccinated subjects (Groups 1 – 4), comparisons will be made relative to the corresponding UAM1 control (for lab values assessed in both studies), combining groups where possible, as described above (e.g., Group 1 & 2, post-dose-1).

Pregnancy test results will be listed.

Abnormal vital signs (heart rate, systolic/diastolic blood pressure, body temperature) will be summarized by group and by time point (day, prior to/following vaccination). The summary will also include the number and percent of subjects with abnormal and clinically relevant vital signs. Vital signs will be listed, and summarized as continuous variables by time point, including change from baseline, by group, and change pre- to post-vaccination for vaccination visits.

Physical exam results throughout the study period will be summarized by presence/absence of abnormal findings, and abnormal physical exam findings will be listed.

